9.4 Estimated Enrollment Period

This study will enroll approximately 220 participants at approximately 20 clinical centers in the U.S. and Canada. It is projected that 16 patients per month will be enrolled, for a total anticipated enrollment period of approximately 14 months.

10 BASELINE EVALUATION AND RANDOMIZATION VISIT

All participants who completed all screening assessments and have not met any exclusion criteria will undergo baseline evaluation and subsequent randomization.

A complete schedule of assessments throughout the study is provided in Appendix A.

10.1 Baseline Evaluation Phase ($\leq 1 \text{ month}$)

Baseline assessments include:

- Clinical evaluation:
 - o Interim history
 - NYHA class assessment
 - o Medication review
 - Physical examination
- Phlebotomy for core laboratory blood samples:
 - Fe studies
 - Fe bioavailability markers
 - o Biomarkers
 - HFN Bio-repository ± HFN Genetic samples (if consented)

- Cardiopulmonary Exercise Test (CPET)
- 6MWT
- Kansas City Cardiomyopathy Questionnaire (KCCQ)

10.2 Randomization (Day 0)

All eligible study participants who successfully completed all screening and baseline evaluations will be randomized within 30 days of informed consent using procedures determined by the CC. Allocated study medication kits will be dispensed to the patient as detailed in Section 8.3.

All randomized participants will receive a written description of the study with contact numbers of study staff to present to their provider(s). Arrangements will be made for an initial phone call within 7 days of starting study medication.

11 FOLLOW-UP EVALUATIONS

11.1 Day 7 Phone Follow-up (± 2 days)

Participants will receive a phone call from study staff at Day 7 to monitor compliance and tolerance to study medication. Specific queries regarding gastrointestinal symptoms will be included. Study staff will be discouraged from specifically asking questions regarding stool discoloration. Phone scripts will be provided by the Coordinating Center.

11.2 Week 8 Clinic Visit (± 5 days)

Participants will be seen in clinic and will undergo the following study procedures:

- Clinical evaluation:
 - o Interim history
 - NYHA class assessment
 - o Medication review and study medication adherence assessment
 - Physical examination
 - o 6MWT
- Kansas City Cardiomyopathy Questionnaire (KCCQ)
- Dispense study medication kits

11.3 Week 16 Clinic Visit (± 5 days)

Participants will be seen in clinic and will undergo the following study procedures:

- Clinical evaluation:
 - o Interim history
 - NYHA class assessment
 - o Medication review and study medication adherence assessment
 - o Physical examination
- Phlebotomy for core laboratory blood samples:

- \circ $\,$ Fe studies and hemoglobin $\,$
- Fe bioavailability markers
- o Biomarkers
- HFN Bio-repository ± HFN Genetic samples (if consented)
- Phlebotomy for local laboratory blood samples:
 - Complete blood count
 - Renal function and liver function (BUN, creatinine, ALT, AST, alkaline phosphatase and total bilirubin)
- Cardiopulmonary Exercise Test (CPET)
- 6 minute walk test
- Kansas City Cardiomyopathy Questionnaire (KCCQ)
- Discontinue study medication

12 OUTCOME DETERMINATIONS

12.1 Primary Endpoint

1. Peak VO₂ (ml/min) as measured by CPET.

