2 EXECUTIVE SUMMARY

Title	IRONOUT-HF: Oral I ron R epletion effects ON O xygen UpTake in H eart F ailure
Indication	Chronic NYHA class II-IV heart failure with reduced left ventricular ejection fraction (LVEF ≤0.40) and iron deficiency (with or without anemia).
Location	Approximately 20 clinical centers in the United States and Canada
Brief Rationale	Therapeutic options to further improve functional capacity and symptoms in HF beyond neurohormonal antagonism are limited. Studies have demonstrated impaired oxidative capacity of skeletal muscle among HF patients, which may contribute to symptoms of breathlessness and persistent fatigue.
	In addition to its role in erythropoiesis, iron (Fe) plays a critical role in skeletal muscle's oxygen (O_2)-storage capacity (myoglobin) and systemic aerobic energy production. As Fe deficiency is common in patients with symptomatic HF, repletion of iron stores may improve submaximal exercise capacity among these patients beyond the effects on erythropoiesis.
	While intravenous Fe repletion in HF patients with mild Fe-deficiency (i.e. Ferritin <100 or Ferritin 100-299 with transferrin saturation <20%) with or without anemia global well-being and functional status, oral Fe repletion has not been studied. Furthermore, the efficacy of oral Fe to replete iron stores in a similar population and its impact on functional capacity, measured objectively by peak VO ₂ , remains unknown.
Primary Objective	Multi-center, randomized, double-blind, placebo-controlled study for 16 weeks duration. To determine if oral iron polysaccharide is superior to oral placebo in improving the peak VO ₂ as assessed by cardiopulmonary exercise testing (CPET) of a broad population patients with HFrEF and Fe deficiency at 16 weeks. Approximately 20 clinical centers in the United States and Canada.
Secondary Objectives	To determine the impact of oral Fe repletion on: a. Submaximal exercise capacity: O ₂ uptake kinetics and ventilatory efficiency as measured by CPET and 6 minute walk distance b. Plasma NT-proBNP c. Health status: KCC Questionnaire (KCCQ)
Study Design	
Treatment	Twice-daily oral polysaccharide iron complex 150 mg versus matching oral placebo for 16 weeks.
Primary Endpoint	Peak VO ₂ (ml/min)

Secondary Endpoints

- O₂ uptake kinetics and ventilatory efficiency as assessed by CPET
 6 Minute walk distance
 Plasma NT-proBNP level

- 4. KCCQ quality of life score

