15.2 Analysis of the Primary Endpoint

A general linear model with the change in peak VO_2 measured at 16 weeks as the response variable and predictor variables including a treatment indicator and the baseline measure of peak VO_2 will be used in the primary analysis. The treatment effect will be determined by the point estimate and 95% confidence interval for the treatment indicator variable.

A secondary analysis of the peak VO₂ outcome will be conducted using a repeated measures analysis. For this analysis all measurement of peak VO₂(including baseline) will be treated as response variables. The following covariates will be included in the regression model treatment group, time period, treatment group * time period interaction, baseline VO₂ and baseline Fe level. An unstructured correlation matrix will be assumed for the repeated measures within subjects. The mixed model repeated measures analysis will be estimated using SAS PROC MIXED.

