15.5 Sample Size Justification

The proposed sample size of 220 subjects will be adequate to address the primary objectives of the study. As in the HFN's PhosphodiesteRasE-5 Inhibition to Improve CLinical Status And

EXercise Capacity in Diastolic Heart Failure (RELAX) clinical trial, the assumed minimally important difference for peak VO₂ is 1.0 ml/kg/min. Based on prior studies within the HFN, a conservative estimate of 2.0 ml/kg/min for the standard deviation for peak VO₂ (ml/kg/min) will be assumed. Using a two-sample t-test a sample size of 172 subjects (86 per group) will provide 90% power to detect the minimally important difference. These calculations assume a common standard deviation of 2.0 ml/kg/min and a two-sided type I error of 0.05. Allowing for 20% missing data would result in a sample size of roughly 108 per group or a total sample size of approximately 220 subjects.

For secondary endpoints, a sample size of greater than 86 subjects per group will provide greater than 90% power to detect differences greater than 0.5 standard deviations for continuous endpoints. These calculations are based on the two-side t-test and assume that the data are normally distributed with a common standard deviation. Similar sample sizes will provide greater than 80% power to detect differences larger than 0.43 standard deviations.

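### The primary endpoint is declared in ml/min but the trial is sized in ml/kg/min, so the stated 90% power is not shown for the declared endpoint

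*Protocol*

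**What the plan says.** Two places in the protocol give the primary endpoint a unit, and they agree. Section 12.1 has "Peak VO₂ (ml/min) as measured by CPET", and the primary endpoint row of the executive summary (section 2) also uses ml/min.

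The primary analysis in section 15.2 is "A general linear model with the change in peak VO_2 measured at 16 weeks as the response variable", with treatment and baseline peak VO₂ as predictors. It gives no unit. Nor do the primary objective (4.1), the design statement (5), the subgroup section (12.3) or the CPET core laboratory section (17.3.2).

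Section 15.5 works in a different unit throughout:
- on the effect, "the assumed minimally important difference for peak VO₂ is 1.0 ml/kg/min";
- on the variability, "a conservative estimate of 2.0 ml/kg/min for the standard deviation for peak VO₂ (ml/kg/min) will be assumed";
- on the result, "a sample size of 172 subjects (86 per group) will provide 90% power to detect the minimally important difference".

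An allowance of 20% for missing data then leads to about 108 per group and about 220 in total.

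**The concern.** Peak VO₂ in ml/min and peak VO₂ in ml/kg/min are different variables. The second is the first divided by body weight. An important difference and an SD on one scale give those on the other only with information about body weight and how it varies between patients. The protocol supplies none: no conversion, no assumed weight, and no difference or SD in ml/min.

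Two things are at stake. First, the stated 90% power belongs to a variable that sections 2 and 12.1 do not name as the endpoint. Second, a treatment effect reported in ml/min would have no stated important difference to be judged against, because the only such figure is weight-indexed.

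**Working it through.** **Inputs from section 15.5:** difference 1.0 ml/kg/min, SD 2.0 ml/kg/min, two-sided alpha 0.05, power 90%, missing data 20%. Allocation is 1:1 (section 5.2).

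**Step 1. Reproduce the protocol's figure on its own scale.**
- Standardised effect: d = 1.0 / 2.0 = 0.50.
- Normal approximation: n per group = 2 × (1.960 + 1.282)² / 0.50² = 84.1, so 85.
- Two-sample t-test: n = 85.03, so 86 per group. Power at 86 per group is 90.3%.
- Missing data: 86 / (1 − 0.20) = 107.5, so 108 per group, 216 in total, which the protocol rounds to about 220.

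All the stated figures reproduce.

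**Step 2. Try to carry this over to ml/min.** Let W be mean body weight in kg and S the SD in ml/min of the quantity analysed. A difference of 1.0 ml/kg/min corresponds to about W ml/min, so d = W / S. Keeping d at 0.50 requires S to be no more than about 2W. Neither W nor S is in the protocol, so everything from here rests on assumed values.

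| Assumed W (kg) | Difference (ml/min) | Largest S for about 90% power at 86 per group (ml/min) |
|---|---|---|
| 70 | 70 | 140 |
| 80 | 80 | 160 |
| 90 | 90 | 180 |
| 100 | 100 | 200 |

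**Step 3. Show how far the answer depends on the missing inputs.** With W assumed to be 80 kg:

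| Assumed S (ml/min) | d = 80 / S | Power at 86 per group | n per group for 90% |
|---|---|---|---|
| 150 | 0.533 | 94% | 75 |
| 200 | 0.400 | 74% | 133 |
| 250 | 0.320 | 55% | 207 |
| 300 | 0.267 | 41% | 297 |

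Over W from 70 to 100 kg and S from 150 to 300 ml/min, power at 86 per group runs from 33% to 99%. This range is not an estimate of the trial's power. It shows that the protocol does not fix the power for the declared endpoint.

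**Step 4. A case in which little changes.** Suppose 2.0 is the SD of the 16-week change, each patient's weight is stable, weight is independent of the indexed change, and weight has a coefficient of variation (CV) of 20–25%. Then d is approximately 0.50 / √(1 + CV²):
- CV 0.20: d = 0.490, power 89.2%.
- CV 0.25: d = 0.485, power 88.5%.

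Under these assumptions the stated power nearly carries over. The protocol gives no basis for choosing between this case and the less favourable rows of Step 3.

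**The case against.** The strongest reply is that the calculation is right, the mismatch may be a matter of wording, and no loss of power is demonstrated. All of that stands. Step 1 confirms the arithmetic, Step 4 shows that the loss could be trivial, and changing the endpoint's unit to ml/kg/min would bring section 15.5 into line without a new calculation. None of it removes the contradiction: as written, the power statement and the endpoint statement concern different variables.

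Several stronger readings are tempting, and the protocol does not support them.

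- **A reader might infer that the trial is badly underpowered**, by treating 2.0 as a cross-sectional SD and letting body size inflate the spread in ml/min. Comparing week-16 values on that spread without adjustment is not the planned analysis, because section 15.2 adjusts for baseline peak VO₂. For example, assume mean weight 90 kg, weight CV 20–25%, mean peak VO₂ 13–14 ml/kg/min, and independence of weight and indexed VO₂. The ml/min SD is then about 297–366. With an assumed baseline to week-16 correlation of 0.7, the adjusted SD is this times √(1 − 0.7²), about 212–261, and power is about 79–61%. At a correlation of 0.9 it is about 130–159, and power is above 95%. Every one of these inputs is an assumption.
- **A reader might infer that fluid loss under diuretic adjustment would distort a weight-indexed result.** In a randomised, blinded trial, weight change biases the comparison only if it differs between arms. If baseline weight is the divisor, it has no effect. The protocol does not name the divisor.
- **A reader might infer that the scale is left open until the data are seen.** Both statements of the endpoint's unit agree on ml/min, section 15.5 is a planning calculation that does not redefine the endpoint, and section 15.1 requires a statistical analysis plan before the data are analysed.
- **A reader might see an error in using a plain t-test when the analysis adjusts for baseline.** At a given SD, adjustment normally adds precision, so leaving it out of the sample size is an ordinary conservative simplification.

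**Conclusion.** The point holds as an inconsistency between the endpoint and the sample size. The stated 90% power (90.3% when recomputed at 86 per group) applies to weight-indexed peak VO₂. For peak VO₂ in ml/min, the endpoint declared in sections 2 and 12.1, neither the power nor the important difference can be derived from the protocol.

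The contradiction itself rests on no assumption. The size of its effect on power cannot be stated, since it depends on body weights and a ml/min SD that the protocol does not give. It should be corrected because it concerns the primary endpoint and the one power statement made for it, and because the correction is cheap.

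**What to change.** Before unblinding, use one unit in sections 2, 12.1, 15.2 and 15.5. There are two ways:

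- **(a) Weight-indexed endpoint.** Change sections 2 and 12.1 to ml/kg/min, so that section 15.5 applies as it stands. State whether the divisor is baseline weight or weight at the visit.
- **(b) Absolute endpoint.** Keep ml/min. In section 15.5, give the important difference in ml/min, the SD of the 16-week change in ml/min (or the baseline-adjusted SD), and the resulting power for the planned 220 participants. Report ml/kg/min as a supportive analysis.

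The protocol does not say which unit was intended, so the choice is the sponsor's. Under either option, section 15.2 should state the unit of the response variable.

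Option (a) costs only wording. Option (b) costs wording, one recalculation and a source for the ml/min SD; section 15.5 refers to prior network studies but quotes figures only in ml/kg/min, so it cannot be assumed that this SD is at hand. The downside of (b) is that the restated power may be less favourable than 90%.

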12.2 Secondary Endpoints

- 1. O2 uptake kinetics and ventilatory efficiency as assessed by CPET
- 2. 6 Minute walk distance
- 3. Plasma NT-proBNP
- 4. KCCQ quality of life

12.3 Pre-specified Subgroups

Pre-defined subgroup analyses of the primary endpoint (change in peak VO_2 at 16 Weeks) for the following sub-population of patients:

- 1. Patients with or without anemia. Anemia is defined as hemoglobin <12 g/dl.
- 2. Patients with or without venous congestion, based on the following criteria:
 - a. JVP>10cm
 - b. Lower extremity edema

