The observed functional benefits in studies of iron repletion summarized below are likely multifactorial. Elegant animal studies have suggested that during Fe repletion, improvements in hemoglobin levels and peak VO₂ evolve in parallel, whereas enhancements in endurance capacity track with the increase in aerobic enzyme activity.^{17, 18, 20} If iron repletion is shown to improve exercise capacity in HF patients *beyond its effects on erythropoiesis*, it will profoundly impact the treatment of HF.

Name of Protein	Functional Site	Status in HF	Biological Functions
Hemoglobin	Red blood cell	\downarrow	O ₂ transport
Myoglobin	Cytoplasm of muscle cells	\downarrow	Facilitation of O ₂ transport
Oxidative enzymes	Mitochondrial inner membrane	\downarrow	Substrate oxidation→NADH, FADH ₂
Respiratory chain proteins	Mitochondrial inner membrane	\downarrow	Electron transfer of $O_2 \rightarrow NADH$, FADH ₂
Soluble Guanylate Cyclase	Vascular smooth muscle cells, cardiomyocytes	\downarrow	Nitric oxidestimulation of cGMP synthesis

Table 2.1. Fe Containing Proteins that are Altered in HF

NADH indicates the reduced form of nicotinamide adenine dinucleotide; FADH2 indicates the reduced form of flavin adenine dinucleotide; cGMP indicates cyclic guanosine monophosphate.

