3.2 Preliminary Studies

Epidemiology and Pathophysiology

The prevalence of Fe deficiency in HF is estimated to be 38-50%.²¹ Anemia is also present in more than one third of HF patients and is associated with increased LV mass, more rehospitalization, and higher mortality.²²⁻²⁴ Among HF patients with anemia, the majority (71%) have depleted Fe stores as measured by bone marrow aspiration.²⁵

Studies in animals and humans without HF have demonstrated that Fe deficiency anemia reduces indices of work capacity (i.e. peak VO₂) by 10-50%.^{18, 26, 27} The correction of Fe deficiency in both anemic and non-anemic patients without HF improves symptoms, quality of life, and exercise performance.¹⁸ Improvements in PGA, quality of life and 6MWD were apparent within 4 weeks of initiation of Fe repletion and were sustained for at least 24 weeks. Beyond the recognized influence of Fe deficiency on erythropoiesis and O₂ utilization in the periphery, in animal models, Fe deficiency has also been associated with direct myocardial effects as described below.²⁸

Direct myocardial effects of iron repletion

Beyond the recognized influence of iron deficiency on erythropoiesis and O₂ storage and utilization in skeletal muscle, iron deficiency has also been associated with ultrastructural changes in cardiomyocytes such as mitochondrial swelling and abnormal sarcomere structure.²⁸ Heart failure patients have lower myocardial iron content and transferrin receptor concentrations than controls,³² and severe iron deficiency leads to LV systolic dysfunction.^{33, 34}

The influence of iron repletion (IV only) on echocardiography-derived LVEF in patients with chronic HFrEF has been reported in 3 small studies and two meta-analyses. Two of the studies^{35, 36} and both meta-analyses,^{37, 38} reported significant improvement in LVEF with iron supplementation (mean improvement +5%). Separation of Δ LVEF in the treatment vs. placebo groups in Toblli et al was evident at 3 months into the trial. A third study by Okonko et al.³¹ demonstrated no significant difference between IV iron repletion and placebo on change in LVEF. In another recent single-center study,³⁹ a large, detectable improvement in echo-derived

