Rationale for Oral Fe Repletion: Oral Fe is safe, inexpensive and readily available in over-thecounter preparations. However, to date there have been no studies of oral Fe repletion to treat Fe deficiency anemia in patients with HF. A single study suggested that oral Fe repletion improved Fe stores and exercise capacityin patients with congenital heart disease.²⁹ In non-HF populations, IV and oral Fe repletion have resulted in similar sustained increases in circulating ferritin levels, transferrin saturations, and hemoglobin concentrations.³⁰ Of note both oral and IV Fe repletion studies demonstrating benefits from Fe repletion have been \leq 16 weeks in duration, with the exception of FAIR-HF, in which the trial duration was 24 weeks but clinical benefits were apparent by 4 weeks. However, the efficacy of *oral* Fe to replete Fe stores in a similar population to FAIR-HF and its impact on functional capacity, measured objectively by peak VO₂, remains unknown. Furthermore, the effects of oral Fe repletion on LV function and prognostic biomarkers, as well as the role of regulatory molecules, such as hepcidin, in modulating response to oral Fe repletion warrant further investigation.

Drug	Authors/ Journal	Subjects Studied	Fe-Def Definition	N	Time	Primary Endpoint	Findings
IV Fe Sucrose	Tobilli JACC 2007	NYHA 3-4 LVEF<0.35	Ferritin <100 ng/ml and/or Tsat<20%	40	5 wks	Δ Hb, Tsat, Cr Clearance	↑ PGAS, ↑6MWD ↓ NT-BNP, ↑LVEF
IV Fe Sucrose	Okonko JACC 2008 ³¹	NYHA 2-3 LVEF<0.35	Ferritin <100 ng/ml or 100-300 with Tsat<20%	35	16wks	Δ peak VO ₂	↑ PGAS, ↓ NYHA ↑ Peak VO₂α∆ Tsat
IV Fe Carboxym	Anker NEJM 2009	NYHA 2-3 LVEF<0.4 Hb 9.5-13.5	Ferritin <100 ng/ml or 100-300 with Tsat<20%	459	24wks	∆ Global Assessment Score	↑ PGAS, ↓NYHA class ↑6MWD Similar benefit in Hb<12 vs. Hb>12

Table 2.2 Previous studies of Fe repletion in heart failure

IV indicates intravenous, PGAS patient global assessment scale; 6MWD six minute walk distance; Hb hemoglobin, Tsat transferrin saturation; QOL quality of life

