4.3 Exploratory Objectives

1. To determine if the following subgroups of patients may derive differential benefit from oral Fe polysaccharide:

- 1) Patients with or without anemia. Anemia is defined as hemoglobin <12 g/dl.
- 2) Patients with or without venous congestion, based on the following criteria:
 - a) JVP>10cm
 - b) Lower extremity edema
- 3) Patients with and without an RER>1.1 during maximum incremental exercise
- 2. To determine change in renal function (creatinine, cystatin C) with iron polysaccharide vs. placebo
- 3. To determine if Fe repletion impacts markers of the RV-PV unit reserve capacity (i.e. VE/VCO2 slope) as assessed on CPET.
- 4. To determine if oral iron repletion influences clinical outcomes: time to death and HF hospitalization

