7.2 Inclusion Criteria

- 1. Age >18 years
- Previous clinical diagnosis of heart failure with current NYHA Class II-IV symptoms LVEF≤0.40 within 2 years prior to consent, and ≥3 months after a major change in cardiac status (i.e. CABG or CRT).
- 3. Serum ferritin between 15-100 ng/ml or serum ferritin between 100-299 ng/ml with transferrin saturation <20%
- 4. Hemoglobin 9.0-15.0 g/dL (males), 9.0-13.5 (females) at time of enrollment
- 5. Evidence-based medical therapy for HF (including beta-blocker and ACE-inhibitor/ARB unless previously deemed intolerant and diuretics as necessary) with ≤100% change in dose for 30 days prior to randomization
 - a. Changes in diuretic dose guided by a patient-directed flexible dosing program are considered stable medical therapy
- 6. Willingness to provide informed consent

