8.7 Randomization, Stratification and Blinding

Randomization will be stratified by anemia status (anemia is defined as hemoglobin <12g/dL). A permuted block randomization method stratified by site will be used to ensure relatively equal distribution of subjects to each arm within each clinical site. Subjects will be randomized using procedures determined by the Coordinating Center (CC).

Blinding of the study, with respect to treatment groups will be preserved by the use of overencapsulation of Fe polysaccharide capsules. The Investigator may be asked at the end of the trial if he/she had obtained any information that may have led to the potential unblinding of treatment

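### Differential benefit by hemoglobin is examined only through a split at 12 g/dL; adding a treatment-by-continuous-hemoglobin model with sex terms would answer this exploratory question with more power at almost no cost.

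*Protocol*

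**What the plan says.** Section 4.3 lists three subgroup questions among the exploratory objectives, introduced by "To determine if the following subgroups of patients may derive differential benefit from oral Fe polysaccharide". Anemia comes first, followed by venous congestion and exercise effort (RER above 1.1). Section 12.3 turns the first two into pre-specified subgroup analyses of change in peak VO2 at 16 weeks. The anemia subgroup reads "Patients with or without anemia. Anemia is defined as hemoglobin <12 g/dl", with no distinction by sex.

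The same threshold is used in section 8.7: "Randomization will be stratified by anemia status (anemia is defined as hemoglobin <12g/dL". Eligibility in section 7.2, by contrast, is sex-specific: "Hemoglobin 9.0-15.0 g/dL (males), 9.0-13.5 (females) at time of enrollment".

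The protocol does not say how a difference between subgroups will be tested. It names no analysis of hemoglobin as a continuous modifier, and it gives neither the expected hemoglobin distribution nor the share of women. The only figure on anemia frequency is for heart failure in general (section 3.2): "Anemia is also present in more than one third of HF patients".

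**The concern.** Hemoglobin is measured in every participant on a continuous scale, over an eligible range of 9.0 to 15.0 g/dL in men and 9.0 to 13.5 g/dL in women. Cutting it at 12 treats 9.5 and 11.9 as the same value, and 11.9 and 12.1 as different ones. If the benefit of iron rises or falls steadily with hemoglobin, a comparison of two groups is a blunt way to detect it, and it cannot show the shape of the relation.

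The question follows from the trial's rationale. The population is iron-deficient with or without anemia, and section 3.1 stresses exercise benefit "beyond its effects on erythropoiesis". Readers will want to know whether any effect depends on baseline hemoglobin. What is at stake is the quality of that exploratory answer, not the primary result.

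Sex needs separate attention. Women's hemoglobin ceiling lies 1.5 g/dL above the cut (13.5 - 12) and men's 3.0 g/dL above it (15.0 - 12), so the two anemia groups will probably differ in sex mix. An apparent effect of hemoglobin could then partly be an effect of sex.

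**Working it through.** **Inputs from the protocol.** Section 15.5 states that "the assumed minimally important difference for peak VO₂ is 1.0 ml/kg/min". It also gives SD 2.0 ml/kg/min, two-sided alpha 0.05, 90% power, 86 evaluable participants per group (172 in total) and 20% missing data. Allocation is 1:1 (section 5.2).

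**The plan's own figure.** n per group = 2 x SD^2 x (1.960 + 1.282)^2 / difference^2 = 2 x 4 x 10.51 / 1 = 84.1, or 85 after rounding up. The exact t-test needs 85.03, hence 86, which gives 90.3% power. Allowing for 20% missing data, 86 / 0.8 = 107.5, or 108 per group and 216 in total, stated as approximately 220. The figure is reproduced. It covers the main effect only; the protocol gives no power for subgroups.

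**Information kept by the split.** For a linear treatment-by-hemoglobin interaction, this is the squared correlation between hemoglobin and the below-12 indicator. For normal hemoglobin it equals phi(z)^2 / [p(1 - p)], where p is the share below 12, z its normal quantile and phi the normal density. At p = 1/3: z = -0.431, phi = 0.364, and 0.132 / 0.222 = 0.595, so about 40% is lost.

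| Assumed hemoglobin distribution | Information lost |
|---|---|
| Normal, 50% below 12 | 36% |
| Normal, 40% below 12 | 38% |
| Normal, 35% below 12 | 40% |
| Normal, 25% below 12 | 46% |
| Normal, 20% below 12 | 51% |
| Truncated at the eligibility limits (mean 12.5-14 men, 12-12.5 women; SD 1.0-1.6; 20-40% women) | 33-58%, mostly 33-45% |
| Uniform over the eligible ranges | 26-28% |

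**Power for a gradient per SD of hemoglobin** (normal approximation, n = 172). The standard error is 2 x 2.0 / sqrt(172) = 0.305. With 60% of the information kept, the split is worth 0.6 x 172 = 103 participants.

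| Gradient per SD (ml/kg/min) | Continuous | Split |
|---|---|---|
| 0.5 | 37% | 25% |
| 0.75 | 69% | 48% |
| 1.0 | 91% | 72% |

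**Power for a gradient per g/dL** (simulation). Assumptions: n = 172, SD 2.0, 64% men; mean hemoglobin 12.7-13.3 in men and 12.0-12.3 in women; SD 1.3 and 1.1; truncated at the eligibility limits.

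| Model | 0.5 per g/dL | 0.75 per g/dL |
|---|---|---|
| Split, no sex terms | about 30% | 54-58% |
| Continuous, no sex terms | 45-48% | 77-79% |
| Split, with sex and treatment-by-sex | 24-27% | 41-52% |
| Continuous, with sex and treatment-by-sex | 39-40% | 68-74% |

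**Sex.** Under these assumptions 18-31% of men and 45-55% of women fall below 12. Across the wider set of truncated distributions, the correlation with sex is 0.16-0.46 for the split and 0.22-0.68 in size for continuous hemoglobin. As a test case, let only sex modify the effect, by 2.0 ml/kg/min. Without sex terms, a false hemoglobin interaction appears in 10-15% of trials with the split and 16-25% with continuous hemoglobin. With sex terms, both fall to about 5-6%.

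**What the split alone can detect.** The standard error of the difference in effects is 2 x 2.0 / sqrt(172 x p(1 - p)), which is 0.610 at p = 0.5 and 0.704 at p = 0.25. Multiplying by 2.80 (1.960 + 0.842), the difference detectable with 80% power is 1.7-2.0 ml/kg/min. Power for a difference of 1.0 is 37% at a 50/50 split and 29% at 25/75.

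**The case against.** The protocol itself supports the cut. It is the randomization stratum, so treatment is balanced within the two groups. It also matches the split that section 3.2 reports for the earlier multicenter intravenous iron trial ("Similar benefit in Hb<12 vs. Hb>12"), which allows a direct comparison. Both reasons stand, and they are why the subgroup should be kept.

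The magnitudes rest on inputs the protocol does not give: the hemoglobin distribution, the share of women and the gradient. Gradients of 0.5 and 0.75 per g/dL imply effects that differ by 3.0 and 4.5 ml/kg/min across 9-15 g/dL (6 x 0.5 and 6 x 0.75), which is large against a minimally important difference of 1.0. The better model still reaches only 39-40% power at the smaller gradient. This also stands: the trial is sized for the main effect, and no choice of model changes that. The statistical analysis plan is not shown and may already contain a continuous model, so the point concerns only what the protocol fixes.

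A reader might go further in four ways that the documents do not support:

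- **That the cut causes the mixing with sex.** It does not. Continuous hemoglobin is more strongly correlated with sex, and the sex terms remove the problem in either form.
- **That the sex-specific ceilings contradict the common cut.** They are entry limits, not definitions of anemia.
- **That benefit will be claimed from one subgroup's p-value.** Section 12.3 prescribes no within-subgroup testing, and section 15.1 states only a general significance threshold.
- **That anemia is the trial's main modifier question.** It is one of three exploratory subgroups, although the only clinical one used to stratify.

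**Conclusion.** The concern holds as a limited point of efficiency. The only hemoglobin analysis that sections 4.3 and 12.3 state is the split at 12 g/dL. For a roughly linear relation this costs 26-58% of the information, with about 40% a reasonable central value. With sex terms in both models, moving to continuous hemoglobin raises interaction power by about 12 to 16 points at a gradient of 0.5 per g/dL (39-40% against 24-27%). At 0.75 per g/dL it is 68-74% against 41-52%.

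These figures depend on linearity, on an assumed hemoglobin distribution and share of women, and on 172 evaluable participants with SD 2.0 ml/kg/min. If the true effect changes abruptly near 12 g/dL, the advantage shrinks or disappears. Modest gradients remain underpowered with either approach. The primary analysis and its sample size are not affected.

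**What to change.** In section 12.3, with a matching line in section 4.3:

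1. Keep the below-12 g/dL subgroup as a display, reported with its interaction estimate and 95% confidence interval.
2. Add one pre-specified exploratory model for change in peak VO2 at 16 weeks, containing treatment, continuous baseline hemoglobin, treatment-by-hemoglobin, sex, treatment-by-sex and baseline peak VO2.
3. Report the estimated treatment effect with its 95% confidence interval across the eligible hemoglobin range, and check linearity with a spline.

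The cost is a few lines of text and one extra model, using data already collected, with no change to visits or randomization. The drawbacks are the linearity assumption, some power spent on the sex terms (45-48% falls to 39-40% at 0.5 per g/dL), and a result slightly less simple than a two-group comparison.
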